1.3 SCHEDULE OF ACTIVITIES (SOA)

Procedures		Phone Screen - ≤ 4 wks before baseline	Screening Visit	Study Visit 1 Day 0	Study Visit 2 Day 28 +/- 10 days	Study Visit 3 Day 56 +/- 10 days	Study Visit 4 Day 84 +/- 10 days	Study Visit 5 Day 112 +/- 10 days	Final Study Visit 6 Day 196 +/- 10 days
Informed consent		X							
Demographics	X	X							
Medical history	X	X							
Nutrition Counselling ¹			X	X	X	X	X	X	
Injection Teaching				X					
Administer study intervention ²				X				X	
Concomitant medication review	X		X					X	
Physical exam (including height and weight) ³		X	X	X	X	X	X	X	X
Waist circumference ⁴			X					X	X
Vital signs ⁵		X	X	X	X	X	X	X	X
Pregnancy test ⁶		X	X	X	X	X	X	X	
Screening labs (CBC, A1C, acute care panel, hepatic panel, mineral panel, ESR, CRP, 25-OH vitamin D, PT, PTT, urinalysis)		X							
Adverse event review and evaluation				X				X	
DXA				X				X	
Metabolic syndrome markers ⁷			X					X	
2-hour Oral glucose tolerance test (OGTT)			X					X	
Blood draw (Hb A1C, Plasma GI hormones: GLP-1, PYY, research samples to be saved)			X					X	
Stool sample collection (optional)			X					X	
Energy intake at buffet meal			X					X	
Appetite score pre and post meal using visual analog scale (VAS)			X					X	
Attention bias to palatable images study		X					X		
Free living physical activity by accelerometry set -up		X					X		
Weight related quality of life (QoL) score			X					X	
Beck Depression Inventory			X					X	
Columbia Suicide Severity Rating Scale			X					X	
Body-Esteem Scale			X					X	
Blood Sample for Secretome Analysis			X					X	

Abbreviated Title: Liraglutide in Teens Post-SG

Version Date: 1/30/23

Complete Case Report Forms (CRFs)		X	X	X	X	X	X	X
-----------------------------------	--	---	---	---	---	---	---	---

1. Participants will meet with Nutrition Staff from the NIH Clinical Center to review instructions on keeping a log of their dietary intake at the Screening Visit, to review the intake log at Study Visits 1 and 5, and to receive standard obesity lifestyle management advice at Study Visits 1, 2, 3, 4, and 5.
2. First dose of liraglutide administered at the end of the visit after injection teaching.
3. Interim medical history for changes in health and limited symptom-directed physical examination, including injection sites at visits 2 through 5.
4. Waist circumference measured by Clinical Center Nutrition Staff.
5. Systolic and diastolic blood pressure measured after 5 minutes of rest.

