Initial management of obesity involves making lifestyle modifications to increase physical activity and adopt a healthy and well-balanced diet. However, most adolescents achieve only mild to moderate weight loss with reduction of BMI by -1 to -2 kg/m² and have difficulty implementing and sustaining their lifestyle changes [29]. Adolescents who continue to have severe obesity or have obesity with complications such as sleep apnea or diabetes despite lifestyle modification are sometimes prescribed pharmacologic agents, but options are limited; Orlistat, a lipase inhibitor is FDA approved for children ≥ 12 years, and phentermine, a norepinephrine reuptake inhibitor for short-term use (12 weeks) is FDA approved for adolescents > 16 years [30, 31]. Both have modest efficacy with approximately 3% mean BMI reduction [30, 31]. Liraglutide, a glucagon-like peptide 1 (GLP1) agonist is the latest medication to be approved for chronic weight management in children 12 years and older with $\text{BMI} \geq 30 \text{ kg/m}^2$. A double-blind, placebo-controlled phase 3 study showed that after 56 weeks, patients treated with liraglutide achieved a statistically significant reduction in BMI SDS of -0.23 compared with no reduction in the placebo group (estimated treatment difference: -0.22; 95% CI, -0.37, -0.08; P =.0022) [32].

Other agents have also been used off-label in some pediatric patients with variable results and unknown long-term outcomes. Consequently, an increasing number of patients with moderate to severe obesity and its comorbidities who fail to lose weight despite lifestyle and pharmacologic intervention are undergoing metabolic and bariatric surgery (MBS), which is currently considered the most effective treatment of severe obesity and its associated comorbidities, and is recommended by both the American Society for Metabolic and Bariatric Surgery (ASMBS) and the American Academy of Pediatrics (AAP) [33, 34].

The two most common surgical approaches used in children and adolescents with obesity are sleeve gastrectomy (SG) and Roux-en-Y gastric bypass (RYGB). In 2015, 66.6% of cases were SG and 28.5% were RYGB among adolescents age 18-21 years who underwent MBS in the

Abbreviated Title: Liraglutide in Teens Post-SG

Version Date: 1/30/23

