
 1. To study the effects of 16 weeks of liraglutide 3.0 mg subcutaneously on change in BMI and fat mass in adolescents who underwent vertical sleeve gastrectomy (SG) ≥ 1 year prior to study initiation but still have obesity or have a recrudescence of obesity after surgery. 2. To compare the effects of liraglutide on BMI and fat mass in enrolled participants who had a poor initial response to SG (<20% BMI reduction at BMI nadir) vs. those with a typical post-SG weight loss ($\geq 20\%$ BMI reduction at BMI nadir) 3. Tolerability and Safety of 3.0 mg liraglutide 	
Change from baseline to 16 weeks in:
 
 1. BMI 2. Proportion reducing BMI by at least 5% and 10% 3. BMI standard deviation score for age and sex (BMIZ) 4. Body weight 
Comparison of changes in BMI and fat mass after 16 weeks of liraglutide in participants who had a poor initial response to SG (<20% BMI reduction at BMI nadir) vs. those with a typical post-SG weight loss ($\geq 20\%$ BMI reduction at BMI nadir)
 
Percentage of participants reaching the top liraglutide dose and all adverse events will be recorded.
	
BMI correlates with adiposity and obesity-related comorbidities such as hypertension, type 2 diabetes, sleep apnea, and dyslipidemia.
 
Measuring the proportion of patients reducing their BMI by at least 5% and 10% will help better differentiate degree of weight loss with drug treatment.
 
Percentage total body fat mass by DXA will be measured because weight loss with drug treatment may be associated with changes in body composition.

Tertiary/Exploratory		

 1. To examine the effects of liraglutide in enrolled participants on changes in body composition, metabolic syndrome markers, energy intake, glucose tolerance, GI hormone concentrations, appetite, free living physical activity, mood, 	
 1. Percentage total body fat mass by DXA 2. Appetite score using visual analog scale (VAS) 3. Attention bias to highly palatable images 4. Energy intake at buffet meal 	
Weight loss with drug treatment may affect obesity-related comorbidities/metabolic syndrome markers such as hypertension, dyslipidemia, glucose intolerance/diabetes.
 
We will examine the effect of liraglutide on

Abbreviated Title: Liraglutide in Teens Post-SG

Version Date: 1/30/23

OBJECTIVES	ENDPOINTS	JUSTIFICATION FOR ENDPOINTS

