1.31 SAMPLE SIZE DETERMINATION

As this is a pilot investigation to determine the sample size of a fully powered investigation, no formal sample size determination is necessary. That said, the study is powered such that it might be able to detect a moderate-to-large difference from treatment. A recent randomized, double-blind, placebo-controlled phase 3 trial of liraglutide for adolescents (age 12 to <18 years) with obesity ($BMI \geq 30 \text{ kg/m}^2$ and $\geq 95^{\text{th}}$ percentile for age and sex) [32] reported a -1.39 kg/m^2 ($SE=0.31$, $n=125$) difference over 1 year of liraglutide treatment. If that effect size is replicated and if a similar SD (3.46) is found in the present study, we estimate that a total sample size of 40 subjects will have 80% power (β) to detect a -1.39 kg/m^2 difference in BMI (effect size = -

Abbreviated Title: Liraglutide in Teens Post-SG

Version Date: 1/30/23

0.4017) at level of significance of 0.05 (1-sided, as we are interested only in BMI loss). See **Table 2**.

t-test - Means: Difference between two dependent means (matched pairs) Tails = 1, $\alpha = 0.05$, Effect size dz = 0.4

[figure not shown]

Table 2, drawn using data obtained using G-Power 3.1.9.2 [90, 91]

We anticipate that virtually all participants who sign consent and are screened will qualify and agree to enroll. We will therefore attempt to recruit and screen in person no more than 50 adolescents, among whom no more than 43 will be treated with liraglutide in hopes of having 40 who complete the study. Based on prior studies in adolescents using liraglutide, we anticipate few dropouts or withdrawals by week 16. In Kelly et al's study of adolescents [32], 119/125 (95%) of those treated with liraglutide remained on-treatment at week 16.

As a pilot investigation, there is no assumption that there will be adequate power for any of the secondary outcomes investigated. We will, however, be able to use the data to determine power in a future randomized controlled trial for these outcomes.

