1.33 STATISTICAL ANALYSES

1.33.1 General Approach

Tabulations will be produced for appropriate demographic, baseline, efficacy, and safety parameters. For categorical variables, summary tabulations of the number and percentage of subjects within each category of the parameter will be presented. For continuous variables, the number of subjects (N), mean, median, standard deviation (SD), minimum, and maximum values will be presented.

Formal statistical hypothesis testing will be performed on endpoints with testing conducted at the 1-sided, 5% level of significance. Summary statistics will be presented, as well as confidence intervals (Cis), as described in the sections below. Trial success will be based on a p-value <0.05.

Covariates to be modeled are pre-specified in the sections below. Results of statistical procedures for efficacy outcomes involving covariates will be presented as adjusted means (least-squares means) with standard errors.

Checks of assumptions (e.g., normality) underlying statistical procedures will be performed and corrective procedures will be applied. It is expected that log transformation will be used for the primary outcome and most secondary outcomes. Percentage data will be arcsin (square root (value)) transformed for analysis.

Unless otherwise noted, all statistical analyses will be performed using SPSS statistical software Version 25 (IBM Corp, Armonk, NY) or higher.

Subject disposition will be tabulated and include the number screened, the number randomized, the number treated in total, the number dosed with liraglutide, the number in each subject population for analysis, and the number who withdrew prior to completing the study and reason(s) for withdrawal.

A by-subject data listing of study completion information including the reason for premature study withdrawal, if applicable, will be made available. Subject disposition will include patients in the Screening Analysis Dataset.

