1.33.3 Analysis of the Secondary Endpoint(s)

There are 2 sets of key secondary endpoints. These analyses are not dependent on findings of the primary endpoint. They will be calculated as changes from baseline to 16-week visit in the ITT dataset:

1. Changes in BMI and fat mass after 16 weeks of liraglutide.
2. Comparison of changes in BMI and fat mass after 16 weeks of liraglutide in participants who had a poor initial response to SG (<20% BMI reduction at BMI nadir) vs. those with a typical post-SG weight loss ($\geq 20\%$ BMI reduction at BMI nadir)

For these analyses, last observation carried forward (LOCF) imputation will be used for missing data. The sample is too small to use any other statistical imputation method accurately. A sensitivity analysis using baseline observation carried forward (BOCF) will also be conducted.

Changes in BMI and fat mass after 16 weeks of liraglutide will be evaluated using paired t-tests of baseline versus 16-week values. Data will be transformed as necessary to meet statistical assumptions of normality.

Comparisons between those who had a poor versus typical post-SG weight loss will be conducted with ANCOVAs with change (16-week minus baseline value) as the dependent factor; group (poor vs. typical weight loss) as the independent factor; and sex, race, age, and height tested as potential covariates.

Tertiary endpoints will be evaluated using similar approaches. For the secretome analysis, paired statistical tests will be applied to each analyte (using parametric or nonparametric statistical approaches as required by the data) to find significant changes in secretome components. The Benjamini-Hochberg procedure will be used to determine the false discovery rate for multiple comparisons.

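### The single-arm paired t-test for hypothesis A cannot separate liraglutide from lifestyle advice or time, so its p<0.05 should not count as efficacy or trial success

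*Combined protocol and SAP*

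**What the plan says.** Secondary objective 1 in the Objectives and Endpoints table is "To study the effects of 16 weeks of liraglutide 3.0 mg subcutaneously on change in BMI and fat mass" in adolescents who still have, or again have, obesity after sleeve gastrectomy. Sections 1.1 and 1.7 describe the trial as an investigation of liraglutide's efficacy. Hypothesis A in Section 1.30 predicts a significant fall in BMI and fat mass after 16 weeks of treatment.

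Section 1.33.3 gives the test: "Changes in BMI and fat mass after 16 weeks of liraglutide will be evaluated using paired t-tests of baseline versus 16-week values". Section 1.33.1 sets "testing conducted at the 1-sided, 5% level of significance" and adds "Trial success will be based on a p-value <0.05". Section 1.33.2 gives a different criterion: the study succeeds if more than 80% complete it.

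There is no control arm. Footnote 1 of the Schedule of Activities (Section 1.3) has every participant meet nutrition staff "to receive standard obesity lifestyle management advice at Study Visits 1, 2, 3, 4, and 5".

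The documents offer two figures for what might happen without an active drug:

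- Section 1.4, on lifestyle modification as initial management, says that "most adolescents achieve only mild to moderate weight loss with reduction of BMI by -1 to -2" kg/m². It gives no time frame and adds that the changes are hard to carry out and sustain.
- Section 1.33.2 reports that BMI rose by 0.19 kg/m² over 1 year on placebo in the phase 3 adolescent liraglutide trial. Section 1.5 says that this group also had lifestyle therapy.

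**The concern.** The objective asks what liraglutide does. The paired t-test asks whether mean BMI moved at all while participants took liraglutide, received monthly advice, and were followed for 16 weeks after being selected for high BMI. The two questions coincide only if everything other than the drug adds up to zero change.

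The nominal 5% error rate, read as the chance of crediting an inert drug, holds only at that one value. If BMI would have drifted down anyway, the chance is higher. If it would have drifted up, the chance is lower, and part of a real drug effect is hidden.

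The plan already recognises this elsewhere. When it sizes the future randomised trial, Section 1.33.2 uses 1.39 + 0.19 = 1.58 kg/m², so it allows for a non-zero change in controls. Hypothesis A makes no such allowance. At stake is whether a significant pilot result is reported as evidence that the drug works, and whether the trial is called a success on that ground.

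**Working it through.** **Inputs.** n = 40, one-sided alpha 0.05, assumed change -1.39 kg/m² and SD 3.46 kg/m² (Section 1.31). The SD follows from the cited standard error: 0.31 × √125 = 3.47.

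**The plan's own figure.** Section 1.31 states: "we estimate that a total sample size of 40 subjects will have 80% power". For a paired t-test the standardised effect is 1.39 / 3.46 = 0.4017, the noncentrality is 0.4017 × √40 = 2.54, and the critical t on 39 degrees of freedom is 1.685. The noncentral t distribution gives power 0.803, so the figure is reproduced. This is power for a total change of -1.39, whatever its source.

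**Rejection rate with an inert drug.** Let b be the background change.

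- Standard error of the mean change = 3.46 / √40 = 0.547.
- The test rejects when the t statistic for the fall exceeds 1.685. At SD 3.46 this is an observed fall of about 1.685 × 0.547 = 0.92 kg/m².
- Rejection probability = P(noncentral t with 39 df and noncentrality -b / 0.547 exceeds 1.685).

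| Background change b (kg/m²) | Noncentrality | Chance of p<0.05 with no drug effect |
|---|---|---|
| +0.19 (cited placebo plus lifestyle, 1 year, non-surgical) | -0.35 | 2.4% |
| 0 | 0 | 5.0% |
| -0.20 | 0.37 | 10% |
| -0.25 | 0.46 | 11.6% |
| -0.5 | 0.91 | 22.8% |
| -1 | 1.83 | 56.0% |
| -2 | 3.66 | 97.4% |

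Simulation with 200,000 replicates gave 2.4%, 4.9%, 56.0% and 97.4% at +0.19, 0, -1 and -2.

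**Sensitivity.** The SD comes from 1-year data, so the 16-week SD is uncertain.

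| Case | +0.19 | -0.5 | -1 | -2 |
|---|---|---|---|---|
| n=40, SD 2.5 (assumption) | 1.7% | 34.4% | 80.0% | >99.9% |
| n=40, SD 4.0 (assumption) | 2.6% | 19.3% | 46.4% | 92.8% |
| n=36, SD 3.46 | 2.5% | 21.3% | 52.2% | 96.0% |
| n=43, SD 3.46 | 2.3% | 23.8% | 58.7% | 98.1% |

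**If the pilot sees exactly what it plans for.** An observed -1.39 with SD 3.46 has a one-sided 95% upper limit of -1.39 + 0.92 = -0.47. Zero change is excluded, but a background fall of 0.5 kg/m² is not.

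**The case against.** The strongest reply is that the test matches the hypothesis as written. Hypothesis A speaks of a decrease after 16 weeks of treatment, and a paired t-test examines that. The protocol calls itself an open-label, non-randomised pilot, treats this as a secondary analysis separate from the primary endpoint, and leaves the controlled comparison to a later trial. The success sentence in Section 1.33.1 is general and does not name hypothesis A. All of this is fair, and it places the fault in the reading of the p-value rather than in the test. It does not remove the fault: the stated objective is the effect of liraglutide, and the plan attaches a success rule to significance.

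A reader might go further and infer that the protocol credits this trial's counselling with -1 to -2 kg/m², so that an inert drug would pass 56 to 97% of the time. The documents do not support that:

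- The Section 1.4 figure concerns adolescents in general, has no time frame, and is not about this trial's counselling.
- Visit 5 advice is given at the outcome visit, so only four advice visits can affect week-16 BMI.
- Section 1.4 calls these participants uniquely resistant to treatment and notes that many regain weight after a nadir at about 1 year. Background drift could therefore be upward.
- The adolescent placebo-plus-lifestyle figure, +0.19, gives a rejection rate below the nominal 5%.

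Nor does +0.19 settle the matter in the plan's favour. It is a 1-year value in adolescents without bariatric surgery, and an early fall could have been followed by regain. In the large adult trial cited in Section 1.5, the placebo group lost 2.8 kg over 56 weeks.

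**Conclusion.** The concern holds as a limit on interpretation. A significant result for hypothesis A shows that BMI or fat mass fell during the treatment period. It does not show that liraglutide caused the fall, and it should not serve as evidence of efficacy or as trial success. The p<0.05 rule in Section 1.33.1 also conflicts with the completion criterion in Section 1.33.2.

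The chance of passing with an inert drug runs from about 2% to 97% across the figures that the documents offer, and no single value can be defended. No 16-week change without the drug is given for adolescents after sleeve gastrectomy. The upper end needs the full general lifestyle effect to occur within 16 weeks in this group. The more modest finding needs much less: a background fall of about 0.20 kg/m² already doubles the nominal 5%.

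These rates assume n=40, SD 3.46 and roughly normal changes on the untransformed BMI scale. They do not carry over to fat mass, for which the documents give neither an SD nor a background figure. The attribution problem applies there equally.

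**What to change.** 1. In Sections 1.30 and 1.33.3, word hypothesis A and its conclusion, for both BMI and fat mass, as change *during 16 weeks of liraglutide plus lifestyle counselling*.
2. In Section 1.33.1, remove p<0.05 as the success rule for efficacy. Keep the feasibility criterion of Section 1.33.2, more than 80% completing, as the single definition of success.
3. Report the mean change in BMI and fat mass with its confidence interval. For BMI, show the interval descriptively beside a stated range of background values that includes +0.19, 0, -0.5 and -1.0 kg/m².
4. Set no cut-off for attributing change to liraglutide. Any such margin would let an uncontrolled study make the claim that item 1 withdraws. A margin of -1.0, for example, would rest on a figure not specific to this population, and the test against it would have only about 17% power at the planned total change of -1.39.

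The cost is a few sentences and one extra line in the results table, with no new visits, data or participants. The downside is that the pilot no longer claims efficacy from this test. That claim is left to the planned randomised trial.

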1.33.4 Safety Analyses

Safety endpoints will be analyzed as summary statistics during treatment in the Safety dataset. For each safety parameter, the last assessment made prior to the first dose of study drug will be used as the baseline for all analyses. AEs will be analyzed based on the drug received.

Adverse events will be coded using the Medical Dictionary for Regulatory Activities (MedDRA). A treatment-emergent AE (TEAE) is defined as an AE that starts or worsens at or during the time of or after the first study drug administration through the final visit. Each TEAE will be counted once only for a given participant. Severity, frequency, and relationship of AEs to study intervention will be presented by System Organ Class (SOC). For SAEs, information will be reported about start date, stop date, severity, relationship, expectedness, outcome, and duration. Adverse events leading to premature discontinuation from the study intervention and TEAEs will be presented in a table or a listing.

Clinical Laboratory Evaluations: All numeric laboratory data including chemistry (such as acute care panel and hematology tests will be summarized at each visit as well as changes from baseline using summary statistics. Laboratory values will be categorized as normal, high, and low, based on normal ranges. Shift from baseline will be summarized at each post-baseline visit.

Abbreviated Title: Liraglutide in Teens Post-SG

Version Date: 1/30/23

Vital Signs: Descriptive statistics for resting heart rate, diastolic blood pressure, systolic blood pressure, temperature, and the change from baseline to each post-baseline visit. The change from baseline to the minimum and maximum post-baseline values will also be summarized by treatment group. Shift tables may also be presented. Clinically significant vital signs will be identified in the eCRF and will be listed.

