Visits 2-4: Each participant will undergo a brief history and directed physical examination to include injection site examination at monthly visits. Weight, height, and blood pressure will be measured at each visit. All participants will be assessed for adverse effects of study drug. Female participants will undergo a repeat pregnancy test at every visit. All participants will meet with Nutrition Staff to receive standardized education on a healthy diet. Used 1-month supply of liraglutide pens will be returned to research team and new 1-month supply of liraglutide will be provided to participant. At visit 4, a wrist accelerometer to measure free living physical activity will be placed and testing on attention bias to highly palatable images will be conducted. They will also receive material to collect stool at home if they choose to turn in stool samples at Visit 5.

Visit 5 (at ~16 weeks): Each participant will undergo a history and physical examination and female participants will undergo a pregnancy test. All participants will then undergo fasting blood work followed by 2-hour oral glucose tolerance testing, questionnaires, testing on appetite, DXA scan, and energy intake measurement at a buffet meal at the NIH Clinical Center. They will meet with Nutrition Staff to review their 1-week food log and receive standardized education on a healthy diet and physical activity. Each participant will have the option to turn in stool samples collected at home or during their clinic visit. Used 1-month supply of liraglutide pens will be returned to research team. Liraglutide will be discontinued at this visit. The wrist accelerometer will be returned.

Visit 6 (off medication, at ~28 weeks): Each participant will undergo a history and physical examination. Weight, height, and waist circumference will be measured.

Abbreviated Title: Liraglutide in Teens Post-SG

Version Date: 1/30/23

INTRODUCTION

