1.7 OVERALL DESIGN

This trial will be a multi-site open-label Phase II non-randomized pilot study involving two US sites: NIH Clinical Center and CNH. [name] and [name] at CNH will be involved in identifying and recruiting potential participants. They will be involved in answering questions about the study from interested patients but will not be screening or obtaining consent from participants. They will also be analyzing identifiable information from participants. All study visits will be conducted at a single site (NIH Clinical Center) to investigate the efficacy of liraglutide, a glucagon-like peptide-1 (GLP1) analogue to promote weight loss in pediatric patients (age 12 to <21y) who continue to have obesity (BMI ≥ 30 kg/m² or BMI $\geq 95^{\text{th}}$ percentile for age and sex) 1 year or more after vertical sleeve gastrectomy (SG) over 16 weeks.

Participants will undergo a telephone screening, followed by a screening visit to assess eligibility. Those found eligible will undergo a baseline evaluation to assess their glucose tolerance, lipids, levels of plasma GI hormones, appetite, body composition, energy intake, free living physical activity (by accelerometry), questionnaire measures, including assessment of weight related quality of life, mood, suicidality, and self-perception of body image. The trial will be divided into two consecutive periods. Period 1 will consist of 5 weeks of dose titration with goal of reaching max dose of 3 mg liraglutide daily with visits every 4 weeks over 16 weeks (including the 5 weeks of titration). The treatment period will then be followed by a 12-week period off study drug ending at week 28.

The primary outcome (change in BMI) will be statistically analyzed after participants have been treated with 3.0 mg daily liraglutide or max tolerated dose at 16 weeks. Secondary outcomes will also be measured at 16 weeks. BMI will be reassessed at follow-up at 28 weeks. There will be no interim analyses. Randomization will be stratified by birth sex assignment (Male versus Female), race (Non-Hispanic Black versus Other), and degree of weight loss after SG (those with typical post-SG weight loss, defined as $\geq 20\%$ BMI reduction versus those with poor post-surgical weight loss response, defined as $< 20\%$ BMI reduction post-SG), since expectation of benefit might differ in those unable to lose weight with SG.

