“Absorption -Following subcutaneous administration, maximum concentrations of liraglutide are achieved at 11 hours post dosing. The average liraglutide steady state concentration (AUC_{τ/24}) reached approximately 116 ng/mL in obese (BMI 30-40 kg/m²) subjects following administration of SAXENDA. Liraglutide exposure increased proportionally in the dose range of 0.6 mg to 3 mg. The intra-subject coefficient of variation for liraglutide AUC was 11% following single dose administration. Liraglutide exposures were considered similar among three subcutaneous injection sites (upper arm, abdomen, and thigh). Absolute bioavailability of liraglutide following subcutaneous administration is approximately 55%.

“Distribution -The mean apparent volume of distribution after subcutaneous administration of liraglutide 3 mg is 20-25 L (for a person weighing approximately 100 kg). The mean volume of distribution after intravenous administration of liraglutide is 0.07 L/kg. Liraglutide is extensively bound to plasma protein (greater than 98%).

“Metabolism -During the initial 24 hours following administration of a single [3H]-liraglutide dose to healthy subjects, the major component in plasma was intact liraglutide. Liraglutide is endogenously metabolized in a similar manner to large proteins without a specific organ as a major route of elimination.

“Elimination -Following a [3H]-liraglutide dose, intact liraglutide was not detected in urine or feces. Only a minor part of the administered radioactivity was excreted as liraglutide-related metabolites in urine or feces (6% and 5%, respectively). The majority of urine and feces radioactivity was excreted during the first 6-8 days. The mean apparent clearance following subcutaneous administration of a single dose of liraglutide is approximately 0.9-1.4 L/h with an elimination half-life of approximately 13 hours, making liraglutide suitable for once daily administration.”

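### The safety section summarises events during treatment but counts treatment-emergent events to Day 196, 12 weeks after liraglutide stops

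*Combined protocol and SAP*

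**What the plan says.** Section 1.33.4 (Safety Analyses) opens with: "Safety endpoints will be analyzed as summary statistics during treatment in the Safety dataset". In its next paragraph it defines a treatment-emergent event as one that starts or worsens at or "after the first study drug administration through the final visit".

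The schedule in 1.3 has the columns "Study Visit 5 Day 112 +/- 10 days" and "Final Study Visit 6 Day 196 +/- 10 days". Its summary of Visit 5 states: "Liraglutide will be discontinued at this visit". Section 1.7 confirms the design: "The treatment period will then be followed by a 12-week period off study drug ending at week 28". The synopsis (1.1) gives the same split, 16 weeks on drug and 12 off.

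Events in the off-drug period are meant to be collected. Section 1.27 calls for adverse-event monitoring at all clinic visits, and 1.28.4 has the investigator ask at each visit about events since the previous one and record time of onset. Section 1.22 says that stopping liraglutide does not by itself end study participation.

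The plan sets no on-treatment cut-off or residual-effect window, and it plans no separate table for off-drug events.

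**The concern.** An analyst building the adverse-event table has to choose between two instructions in one section. Following the explicit definition labels as treatment-emergent every event up to 12 weeks after the planned last dose. Residual exposure does not explain a window of that length, because 1.17.1 gives "an elimination half-life of approximately 13 hours".

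Tolerability and safety of liraglutide 3.0 mg is a key secondary endpoint (1.1, 1.30). In a randomised trial a long window adds background events to both arms, and the comparison partly absorbs them. Here there is one arm, so background events go straight into the reported frequencies. The provision in 1.33.4 to analyse events by drug received separates nothing when everyone receives the same drug. Efficacy is read at week 16 (1.33.3), so benefit and harm would also be reported over different periods.

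**Working it through.** **Inputs.** Visit 5 at Day 112 and Visit 6 at Day 196, each with a window of 10 days either way (1.3); drug stopped at Visit 5 (1.3); 16 weeks on and 12 off (1.1).

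**Reproducing the plan's own split.** 112/7 = 16 weeks; 196/7 = 28 weeks; (196 − 112)/7 = 12 weeks. This agrees with 1.1 and 1.7.

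**Off-drug share of the treatment-emergent window, (V6 − V5)/V6:**
- Nominal: 84/196 = 42.9%.
- Smallest within the visit windows (Visit 5 at Day 122, Visit 6 at Day 186): 64/186 = 34.4%.
- Largest (Visit 5 at Day 102, Visit 6 at Day 206): 104/206 = 50.5%.

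**Early stoppers followed to week 28, (28 − s)/28:**
- Stop at week 4: 24/28 = 85.7%.
- Stop at week 8: 20/28 = 71.4%.
- Stop at week 12: 16/28 = 57.1%.

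Reading the final visit as the participant's own last visit does not remove the problem. Someone who stops at week 4 and is last seen at week 16 is off drug for (16 − 4)/16 = 75% of the window.

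**Illustration of the effect on a reported percentage.** The documents give no event rate for this population, so this rests on assumptions. Section 1.6.1 cites an adolescent trial in which 89% on liraglutide and 85% on placebo had an event during treatment; 1.4 gives 56 weeks for that trial. Assume that these percentages refer to 56 weeks, that hazards are constant, and that the placebo hazard applies once drug stops.
- Liraglutide hazard: −ln(0.11)/56 = 0.0394 per week. Placebo hazard: −ln(0.15)/56 = 0.0339 per week.
- Any event in 16 weeks on drug: 1 − exp(−16 × 0.0394) = 46.8%.
- Any event in 28 weeks: 1 − exp(−16 × 0.0394 − 12 × 0.0339) = 64.6%.
- The same steps with the gastrointestinal figures in 1.6.1 (64.8% and 36.5%) give 25.8% and 32.7%.

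The result depends on the hazard model. Take background alone, from the 85% placebo figure. A constant hazard gives 42% with at least one event by week 16 and 61% by week 28. If people differ in susceptibility (gamma frailty with variance 1, an assumption), solve 1/(1 + 56h) = 0.15, so h = 0.101 per week. Then 1 − 1/(1 + 16h) = 62% and 1 − 1/(1 + 28h) = 74%. The increment falls from about 20 points to 12.

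**The case against.** Following events to the end of the study is a defensible, conservative choice in a descriptive pilot treating at most 43 people. That stands: collection after treatment should continue. The defect lies in the label and the missing split.

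A reader might infer that off-drug events will be attributed to liraglutide. The documents do not support that. Section 1.33.4 also reports relationship to study drug, and 1.28.3.2 grades relationship partly on timing. Relationship is, however, an open-label investigator judgement and does not replace a defined window for the frequency table.

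A reader might infer that the wide window distorts the comparison with label rates in 1.28.3.3. That section concerns expectedness and unanticipated problems as judged by the investigator and reviewed by the Safety Officer. It does not say that the treatment-emergent table feeds that judgement. A 16-week cut-off would not create like-for-like rates anyway, since the cited adolescent trial ran 56 weeks and the label table in 1.17.2.2 states no window.

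Off-drug ascertainment is also thinner: one visit in 12 weeks, against four-weekly visits and three weekly calls on drug. The adverse-event row of the schedule shows no clear mark at Visit 6, though that table did not extract cleanly and 1.27 and 1.28.4 call for inquiry at every visit. Each event counts once per participant, so an off-drug recurrence of an event already counted adds nothing, and gastrointestinal events probably cluster in titration. The constant-hazard illustration therefore probably overstates what would be recorded off drug.

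**Conclusion.** The contradiction within 1.33.4 is real, and nominally 43% of the treatment-emergent window is off drug (34% to 51% across the visit windows, more for early stoppers who stay in follow-up). These shares are schedule arithmetic and need no model.

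The consequence is limited to the adverse-event frequencies. It would be too strong to say that the whole tolerability endpoint is compromised: the objectives table also defines it by the percentage reaching the top dose, which this window does not touch, and events that lead to stopping drug are likewise unaffected.

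How far the reported percentages would rise cannot be fixed from the documents. The projections above show direction only and depend on the assumed hazards. This is a minor point, worth settling before the tables are produced.

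**What to change.** Reconcile the two sentences in 1.33.4.

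1. Define an on-treatment window from first dose to last dose plus a short margin. The sponsor should choose and state the margin, taking account of the half-life and the safety visit about 14 days after last dose in 1.23. A margin shorter than that would file findings that first arise at that visit as off-drug.
2. Make events with onset or worsening in that window the main tolerability summary.
3. Tabulate later-onset events separately as off-drug follow-up, and keep every event in the listings.

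The cost is one table split, using onset times already collected under 1.28.4. The downside is that a drug-related event recognised late would appear in the follow-up table; the relationship grading and the full listing keep it visible.
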